8.1.2. Summary Measure

- Change in markers of intestinal mucosal damage samples from blood.
- Changes in Bacterial markers of translocation.

8.1.3. Population of Interest

The exploratory efficacy analyses will be based on the evaluable population, unless otherwise specified.

8.1.3.1. Statistical Analyses / Methods

Unless otherwise specified, endpoints defined in Section 8.1.1 will be summarised using descriptive statistics and listed.

Details of the planned displays are provided in Appendix 8: List of Data Displays and will be based on GSK data standards and statistical principles.

8.1.3.2. Statistical Methodology Specification

There will be no planned statistical analysis.

10. APPENDICES

10.1. Appendix 1: Schedule of Activities

10.1.1. Protocol Defined Schedule of Events

Healthy Participants (Group 1)

Procedure	Screening	Treatment P	eriod [Out pat 1 day)	Notes		
		D1	D8	D15		
Review of inclusion/ exclusion criteria and informed consent	X					
Demography	X					
Medical history (includes substance and alcohol usage at screening) and Medication history	X					
Substance testing (urine)	X				Substances: [Recreational Drugs and Alcohol]	
HIV, Hepatitis B and C screening	X				If test otherwise performed within 3 months prior to study entry, testing is not required	
Laboratory assessments	X					
Pregnancy test (WOCBP only) (urine)	X	(X)			Only performed again on Day 1 if patient at risk of pregnancy at or since screening	
Blood sampling for biomarkers		X			20ml of blood will be sampled in a single draw on one day, preferably Day 1	
Stool sample collection		X			Participants will be given a collection container at screening to bring with them on Day 1.	
Brief physical examination including measurements of height and weight Vital Signs (systolic and diastolic blood	X	X	X	X	BMI calculated from height and weight at screening only Examinations should be conducted the day after intestinal permeability measurement.	
pressure and heart rate) Medical review (assessment of health status)		X	X	X	Monitor for signs and symptoms of gastro-intestinal infections and other emergent issues	

Procedure	Screening	Treatment Po	eriod [Out pat 1 day)	Notes	
		D1	D8	D15	
STM Training	X				Refresher training may be provided as needed
Intestinal permeability measurement:					Please refer to SRM for full information
STM administration followed by a 24-		X	X	X	Intestinal permeability measurement to be performed
hour urine collection					at home the day before the study visit.
AE/SAE and Concomitant medication	(V)	,		、	Day 1 will include concomitant medication review
reviews	(X)	——		→	only

Thermal Injury Participants (Group 2)

0		Treatment Period [ICU Days] (+/4 hours)							6 mon								
Procedure	D1 (≤ 24 hr of admission)	D2	D3	D4	D5	D6	D7	D8	D9	D 10	D 11	D 12	D 13	D 14	D28 (± 3 days)	(± 14 days)	Notes
Review of inclusion/ exclusion criteria and informed consent	X																Participants will be co- consented to the SIFTI-2 study
Medical history (includes substance and alcohol usage) and Medication history	X																
Substance testing (urine)	X																Substances: [Recreational Drugs, Alcohol]
Pregnancy test (WOCBP only) (urine)	X															X	To be repeated at 6 months prior to final STM administration
HIV, Hepatitis B and C screening	X																If test otherwise performed within 3 months prior to study entry, testing is not required
Initial assessment of Burns	X																Calculation of %TBSA Location of thermal injury and depth
Fluid balance (total input/output)	X	X	X	X	X	X	X	X	X	X	X	X	X	X	X*		Daily (over 24 hr) *only if participant still admitted
Intestinal permeability measurement: STM administration followed by a 24- hour urine collection	X		X		X		X		X		X		X		Х	X	Measurements every 48 hours from first measure. Preference: D1, 3, 5, 7, 9, 11, 13. Otherwise: D2, 4, 6, 8, 10, 12, 14. Please refer to SRM for full method.

Brief Physical Examination														X	X	Following final intestinal permeability measurement. Can be omitted if patient is still admitted to hospital.
Stool sample collection		(A	$\leftarrow = = = = = = = = = = = = = = \Rightarrow \qquad \qquad X \qquad X$ (A sample of the first stool produced following admission)									X	Time to first stool collection; preferably on Day 1. Then on Days 14 and 28 and 6 months			
Wound Healing Assessments													X	X	X	This is to assess time to 95% wound healing
AE/SAE and Concomitant medication reviews	X	←===============								X	AE/SAE monitoring will begin after the first administration of STM					

Planned time points for all safety assessments are provided in the SoA and summarised here.

	When conducted									
Safety Assessment	Healthy Participants	Thermally injured participants								
Laboratory tests	Screening. Only repeated if clinically indicated in the opinion of the investigator.	Only if clinically indicated.								
Brief Physical Examination including Vital Signs Recording	Screening, Day 1, Day 8, Day 15	As a part of routine clinical care whilst admitted (not protocol specified). Following day 28 and 6-month intestinal permeability measurements (if patient not still admitted)								
Detection of AEs	Day 1, Day 8, Day 15	Throughout the study								
Assessment of health status	Screening, Day 1, Day 8, Day 15	Not required								

10.2. Appendix 2: Assessment Windows

No visit slotting will be done.

10.3. Appendix 3: Study Phases and Treatment Emergent Adverse Events

10.3.1. Study Phases

10.3.1.1. Study Phases for Concomitant Medication

Study Phase	Definition
Prior	If medication end date is not missing and is before 28 days prior to screening visit
Concomitant	Any medication that is not a prior

NOTES:

• Please refer to Appendix 6: Reporting Standards for Missing Data for handling of missing and partial dates for concomitant medication. Use the rules in this table if concomitant medication date is completely missing.

10.4. Appendix 4: Data Display Standards & Handling Conventions

10.4.1. Reporting Process

Software				
The currently support	The currently supported versions of SAS software 9.4 or higher will be used.			
Reporting Area				
HARP Server	: Uk1salx00175\arprod\nocompound\mid206243			
HARP Compound	: No Compound			
QC Spreadsheet : Uk1salx00175\arwork\nocompound\mid206243\Documents				
Analysis Datasets	Analysis Datasets			
Analysis datasets will be created according to IDSL standards.				
Generation of RTF Files				
RTF files will be generated for SAC.				

10.4.2. Reporting Standards

All data displays (Tables, Figures & Listings) will use the term "Subject" which reflects CDISC and GSK Data Display Standards terminology.

General

- The current GSK Integrated Data Standards Library (IDSL) will be applied for reporting, unless otherwise stated (IDSL Standards Location: https://spope.gsk.com/sites/IDSLLibrary/SitePages/Home.aspx):
 - 4.03 to 4.23: General Principles
 - 5.01 to 5.08: Principles Related to Data Listings
 - 6.01 to 6.11: Principles Related to Summary Tables
 - 7.01 to 7.13: Principles Related to Graphics
- Do not include subject level listings in the main body of the GSK Clinical Study Report. All subject level listings should be located in the modular appendices as ICH or non-ICH listings

Formats

- GSK IDSL Statistical Principles (5.03 & 6.06.3) for decimal places (DP's) will be adopted for reporting of data based on the raw data collected, unless otherwise stated.
- Numeric data will be reported at the precision collected on the eCRF.
- The reported precision from non eCRF sources will follow the IDSL statistical principles but may be adjusted to a clinically interpretable number of DP's.

Planned and Actual Time

- Reporting for tables, figures and formal statistical analyses:
 - Planned time will be used in figures, summaries, statistical analyses and calculation of any derived parameters, unless otherwise stated.
 - The impact of any major deviation from the planned assessment times and/or scheduled visit days on the analyses and interpretation of the results will be assessed as appropriate.
- Reporting for Data Listings:
 - Planned and actual time will be shown in listings (Refer to IDSL Statistical Principle 5.05.1).
 - Unscheduled or unplanned readings will be presented within the subject's listings.

CONFIDENTIAL

Unscheduled Visits	Unscheduled Visits			
Unscheduled visits	Unscheduled visits will not be included in summary tables and/or figures.			
All unscheduled vi	All unscheduled visits will be included in listings.			
Descriptive Summary	Descriptive Summary Statistics			
Continuous Data	Continuous Data Refer to IDSL Statistical Principle 6.06.1			
Categorical Data	Categorical Data N, n, frequency, %			
Graphical Displays				
Refer to IDSL Statistical Principals 7.01 to 7.13.				

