The lactulose-to-mannitol ratio is traditionally used to assess small intestinal permeability and sucralose to assess colonic permeability. Lactulose, mannitol and sucralose [henceforth referred to as sugar test material (STM)] will be intermittently administered enterally for the purpose of intestinal permeability measurement to examine permeability at different points along the GI tract and is described in Section 7. It is important to note that the administration of the STM is not therapeutic (lactulose and mannitol can be used as laxatives, however the amount in the STM is sub-therapeutic) and as such should be regarded as a non-investigational medicinal product (NIMP) [[Guidance Documents Applying Investigational Medicinal Products \(NIMPS\)](#), 2011].

An internal preliminary data review will be conducted. This review is described in Section 5.4.4.

Number of Participants:

Table 1 in Section 5.2 described the number of participants proposed for the study. Sample size is based on feasibility. No formal calculation of power or sample size has been performed, but a sample size of 15 healthy participants and 25 thermal injury participants ($\geq 15\%$ TBSA) should be sufficient to provide useful estimates of variability in lactulose:mannitol ratios, and any change in L/M ratio over time.

Treatment Groups and Duration:**Group 1: Healthy Participants**

The total duration of this study for healthy participants will be approximately two weeks, in addition to the screening window:

- Screening: up to 28 days before Day 1
- Day 1: study start and assessments will be performed
- Day 8 and Day 15

Group 2: Thermally injured participants

Thermal injury participants will be asked to participate for a total of 6 months (plus or minus 14 days).

- There will be no screening period. Thermal injury participants will be recruited within 24 hours of their admission to the burns unit at the study site.
- Intense monitoring phase: Assessments will be performed on alternate days for the first 14 days following study enrolment. If the participant is discharged prior to 14 days, the intense monitoring phase will end, but the participant will remain enrolled in the study.
- Convalescent monitoring phase: Assessments at 28 days and 6 months will be made on an outpatient basis if the participant has already been discharged from hospital.

Exception to monitoring periods:

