2.2. Thermal Injury Participants (Group 2)

Procedure	D1 (≤ 24 hours of admission)	Treatment Period [ICU Days] (+/-4 hours)														6 months (± 14 days)	Notes	
		D2	D3	D4	D5	D6	D7	D8	D9	D10	D11	D12	D13	D14	D28 (± 3 days)			
Review of inclusion/exclusion criteria and informed consent	X																	Participants will be co-consented to the SIFTI-2 study
Medical history (includes substance and alcohol usage) and Medication history	X																	
Substance testing (urine)	X																	Substances: [Recreational Drugs, Alcohol]
Pregnancy test (WOCBP only) (urine)	X																X	To be repeated at 6 months prior to final STM administration

Procedure	D1 (≤ 24 hours of admission)	Treatment Period [ICU Days] (+/4 hours)														6 months (± 14 days)	Notes	
		D2	D3	D4	D5	D6	D7	D8	D9	D10	D11	D12	D13	D14	D28 (± 3 days)			
HIV, Hepatitis B and C screening	X																	If test otherwise performed within 3 months prior to study entry, testing is not required
Initial assessment of Burns	X																	Calculation of %TBSA Location of thermal injury and depth
Fluid balance (total input/output)	X	X	X	X	X	X	X	X	X	X	X	X	X	X	X*		Daily (over 24 hr) *only if participant still admitted	
Intestinal permeability measurement: STM administration followed by a 24-hour urine collection	X		X		X		X		X		X		X		X	X	Measurements every 48 hours from first measure. Preference: D1, 3, 5, 7, 9, 11, 13. Otherwise: D2, 4, 6, 8, 10, 12, 14. Please refer to SRM for full method.	
Brief Physical Examination															X	X	Following final intestinal permeability measurement. Can be omitted if patient is still admitted to hospital.	

Procedure	D1 (≤ 24 hours of admission)	Treatment Period [ICU Days] (+/-4 hours)														6 months (± 14 days)	Notes		
		D2	D3	D4	D5	D6	D7	D8	D9	D10	D11	D12	D13	D14	D28 (± 3 days)				
Stool sample collection		←=====→ (A sample of the first stool produced following admission)												X	X	X	Time to first stool collection; preferably on Day 1. Then on Days 14 and 28 and 6 months		
Wound Healing Assessments																X	X	X	This is to assess time to 95% wound healing
AE/SAE and Concomitant medication reviews	X	←=====→														X	AE/SAE monitoring will begin after the first administration of STM		

- The timing and number of planned study assessments may be altered during the course of the study based on newly available data or factors outside of the study such as priority medical care to ensure appropriate monitoring.

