4. OBJECTIVES AND ENDPOINTS

Objective	Endpoint
Co-Primary	
1. To determine the impact of thermal injury on the magnitude of small intestinal permeability change as soon as possible following injury compared to healthy participants	
 Lactulose/Mannitol (L/M) ratio at entry
2. To characterise the effect of thermal injury on small intestinal permeability over time and establish the clinical and demographic factors which can influence it	
 Changes in L/M ratio over time
Exploratory	
1. To determine the impact of thermal injury on colonic permeability as soon as possible following injury compared to healthy participants	
 Fractional excretion of sucralose at entry
2. To characterise the effect of thermal injury on colonic permeability over time	
 Changes in the fractional excretion of sucralose over time

Objective	Endpoint
3. To assess the relationship between severity of a participant's condition following thermal injury and changes in intestinal permeability†	
 • Number of ventilator-free days • Number of vasopressor-free days • Number of hemofiltration-free days • Number of episodes of confirmed infection and sepsis • Number of surgical interventions • Total length of hospital stay • Calculate critical care and thermal injury severity scores
4. To assess plasma and urine biomarkers of intestinal permeability, bacterial translocation and renal tubular dysfunction following thermal injury†	
 • Change in markers of intestinal mucosal damage samples from blood • Change in urine protein:creatinine and urine albumin:creatinine ratios
5. To assess the impact of thermal injury and intestinal permeability on the intestinal microbiome compared to healthy participants	
 • Changes in microbiome of acute and convalescent stool samples
6. To assess the impact of pre-existing co-morbid conditions on intestinal permeability and clinical outcome following thermal injury†	
 • Medical history and drug history at the time of admission
7. To assess wound healing	
 • Time to wound recovery (e.g. 95%)

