6.3.3. Other Inclusions

3. Admission to the burn centre (study site) ≤ 24 hours of injury.

4. Able to take enteral fluids either orally or via a nasogastric tube (depends on facial burn damage).

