10.8.5. Efficacy Tables

Efficacy: Tables							
No.	Population	IDSL / Example Shell	Title	Programming Notes	Deliverable [Priority]		
L/M ratio	L/M ratio						
2.1.	Evaluable	EFF_T1	Summary of Absolute L/M Ratio Values	Summary by: Study group and Visit Page by: Timepoint	SAC		
2.2.	Evaluable	EFF_T1	Summary of Change in L/M Ratio Values	Note: CFB, Summary by: Study group and Visit, Page by: Timepoint	SAC		
2.3.	Evaluable	EFF_T1	Summary of %Change in L/M Ratio Values	Note: %CFB, Summary by: Study group and Visit, Page by: Timepoint	SAC		
Fraction	Fractional excretion of sucralose						
2.4.	Evaluable	EFF_T1	Summary of Fractional Excretion of Sucralose Values	Summary by: Study group and Visit, Page by: Timepoint	SAC		
2.5.	Evaluable	EFF_T1	Summary of Change in Fractional Excretion of Sucralose Values	Note: CFB, Summary by: Study group and Visit, Page by: Timepoint	SAC		
2.6.	Evaluable	EFF_T1	Summary of %Change in Fractional Excretion of Sucralose Values	Note: %CFB, Summary by: Study group and Visit, Page by: Timepoint	SAC		

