10.8.6. Efficacy Figures

Efficacy	Efficacy: Figures						
No.	Population	IDSL / Example Shell	Title	Programming Notes	Deliverable [Priority]		
L/M ratio	L/M ratio						
2.1.	Evaluable	EFF_F1	Individual Plot of Absolute L/M Ratio Values Over Time for Healthy Subjects.	Y-axis: Absolute Values Plot by Timepoint	SAC		
2.2.	Evaluable	EFF_F2	Individual Plot of Absolute L/M Ratio Values Over Time for TI Subjects.	Y-axis: Absolute Values Plot by Timepoint Average value of Healthy Subjects will be used as reference line.	SAC		
2.3.	Evaluable	EFF_F2	Individual Plot of %Change L/M Ratio Values Over Time for TI Subjects.	Y-axis: %CFB Values Plot by Timepoint Average value of Healthy subjects will be used as reference.	SAC		
Fraction	al excretion of s	ucralose					
2.4.	Evaluable	EFF_F1	Individual Plot of Absolute Sucralose Values Over Time for Healthy Subjects.	Y axis: Absolute Values Plot by Timepoint	SAC		
2.5.	Evaluable	EFF_F2	Individual Plot of Absolute Sucralose Values Over Time for TI Subjects.	Y axis: Absolute Values, Plot by Timepoint Average value of Healthy subjects will be used as reference.	SAC		
2.6.	Evaluable	EFF_F2	Individual Plot of %Change Sucralose Values Over Time for TI Subjects.	Y axis: %CFB Values Plot by Timepoint Average value of Healthy subjects will be used as reference.	SAC		

L/M ratio	L/M ratio and Fractional excretion of sucralose					
2.7.	Evaluable	EFF_F3	Individual Plot of Absolue L/M ratio and Sucralose Values Over Time for TI Subjects.	Y axis: Absolute Values Plot by Timepoint Average values of Healthy subjects will be used as reference.	SAC	
2.8.	Evaluable	EFF_F3	Individual Plot of %Change L/M ratio and Sucralose Values Over Time for TI Subjects.	Y axis: %CFB Values Plot by Timepoint Average values of Healthy subjects will be used as reference.	SAC	

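### No planned output for thermally injured participants shows time since injury, so profiles at the same planned day can be misaligned between participants by up to about 48 hours

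*SAP*

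**What the plan says.** **Time axis.** SAP 10.4.2 sets the default: "Planned time will be used in figures, summaries, statistical analyses and calculation of any derived parameters, unless otherwise stated". Nothing in the display lists or mock shells overrides it. The TI figures, such as "Individual Plot of Absolute L/M Ratio Values Over Time for TI Subjects" (Figure 2.2), follow planned days, and the efficacy tables are specified as "Summary by: Study group and Visit". Study Day (SAP 10.5.1) has the first STM dose as its origin.

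**Entry timing.** Protocol 6.3.3 requires "Admission to the burn centre (study site) ≤ 24 hours of injury". The Protocol Synopsis adds: "Thermal injury participants will be recruited within 24 hours of their admission to the burns unit at the study site". In Protocol 2.2 the header of the first study day begins "D1 (≤ 24 hours of admission". The same table allows two test schedules: "Preference: D1, 3, 5, 7, 9, 11, 13. Otherwise: D2, 4, 6, 8, 10, 12, 14". Tests then follow at 48-hour intervals.

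**Purpose.** The first co-primary objective concerns permeability "as soon as possible following injury compared to healthy participants". The first study aim is the size and time course of the change, to guide when and for how long a future product would be given. The background expects permeability to climb quickly after a burn and fall over about two weeks.

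**The concern.** The scientific clock starts at the burn, but the reporting clock starts at a protocol day or at the first STM dose. The gap between the two differs from person to person, and no table, figure or listing reports it.

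The individual profiles carry most of the information here. SAP 1.1 puts the number of TI participants at 3, SAP 6.1.4 rules out formal analysis, and SAP 1.3 says nobody reached Day 28, so all TI data come from the acute phase. If one participant was first tested a few hours after the burn and another nearly two days after, their points sit at the same x position. A reader comparing the curves could take a difference in delay for a difference between patients, or misjudge when after injury permeability is high. The percent-change figures add to this, because each divides by an entry value taken at an unreported time after injury.

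**Working it through.** **1. The plan's own figures.** The documents state no maximum time from injury to entry test, so there is none to reproduce. The 3-fold change used in step 5 comes from the power illustration in Protocol 10.2, which does reproduce: ln 3 = 1.099; standard error = 1.15 × √(1/25 + 1/15) = 0.376; noncentrality = 1.099/0.376 ≈ 2.93; with 38 df and two-sided 0.10, power is 89.0% against the stated 89%. Timing does not enter that calculation.

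**2. Injury to first test (hours), from the protocol's limits.** The Day 2 limits are inferred from how Day 1 is defined. The ±4-hour visit window is left out.

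| Start | Injury to admission | Admission to test | Injury to test |
|---|---|---|---|
| Day 1 | 0 to 24 | 0 to 24 | 0 to 48 |
| Day 2 | 0 to 24 | 24 to 48 | 24 to 72 |

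**3. Spread at one planned day.** Day 1: 48 − 0 = 48 hours. Day 2: 72 − 24 = 48 hours. Both equal one 48-hour sampling interval, or 2 of the 12 days from Day 1 to Day 13.

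**4. Effect on a curve.** Planned time equals time since injury minus that participant's own entry delay. Tests run at 48-hour steps from the first one, so the delay is a constant for each participant. It moves all of that participant's points sideways by the same amount and leaves slope, spacing and shape as they were. Only alignment between participants suffers.

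**5. Illustrative size in L/M.** Assume an R-fold rise that decays log-linearly to normal over T days. A 2-day offset is then worth R^(2/T). With R = 3 and T = 14, 3^(2/14) = 1.17, about 17%. The decay model and T are assumptions, so the range matters:

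| Rise R | T = 14 days | T = 7 days |
|---|---|---|
| 2-fold | 1.10 | 1.22 |
| 3-fold | 1.17 | 1.37 |
| 5-fold | 1.26 | 1.58 |
| 10-fold | 1.39 | 1.93 |

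On the log scale the 17% is ln 1.17 = 0.157, or 0.157/1.15 = 0.14 of the between-subject SD in Protocol 10.2.

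**6. Do existing provisions cover it?** SAP 10.4.2 promises to assess major departures from planned times, but a late entry within the limits is not a departure. It also puts actual times in listings, but a clock time without the time of injury does not give time since injury. Changing from planned day to actual Study Day would not help either, since that origin is the first STM dose.

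**The case against.** The strongest reply is that little depends on this. The report covers three people, plotted individually, with no model, AUC or test. The endpoints are worded as L/M at entry and change over time, and the first objective accepts a variable delay by asking only for the earliest feasible test. SAP Table 1 records that development of the molecule has ended, so the dosing-timing aim has lost its immediate use. Each L/M value pools 5 or 24 hours of urine, which limits time resolution anyway. All of this stands, and it keeps the point small.

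The reply also has force on data. The Day 1 burn assessment in Protocol 2.2 lists %TBSA, location and depth, not time of injury. Inclusion criterion 3 needs only that the delay to admission was at most 24 hours. TI biomarker blood is drawn in SIFTI-2, whose time fields these documents do not show. The fix must therefore allow for approximate or missing times.

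A reader might go further and infer that participants at one planned day can be 72 hours apart. The documents do not support that. The fallback tests are planned for Days 2, 4, 6 and so on, SAP 10.2 rules out visit slotting, and SAP 4.2 sets baseline to missing when Day 1 is absent. A Day 2 starter therefore appears at Day 2, and 72 hours is a maximum delay, not a spread. It would become a spread only if the first dose were relabelled Day 1; the Study Day origin leaves some ambiguity, but the other rules point against it.

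A reader might also suppose that misalignment during the early rise could hide the whole 3-fold change. The documents give no rise time, so no such figure can be derived.

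**Conclusion.** The point holds as a weakness of display and interpretation. No planned output shows time since injury, and permitted entry times leave TI participants misaligned by up to about 48 hours at the same planned day. Individual curve shapes are intact.

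The 48 hours follows from the protocol's own limits, with Day 2 read as the day after a Day 1 defined from admission. The 17% is illustrative only and rests on an assumed 3-fold rise with log-linear decay over 14 days; for rises of 2- to 10-fold resolving in 7 to 14 days, the same offset is worth 1.10- to 1.93-fold. The documents do not give the actual delays of the three participants, so the realised misalignment may be much smaller. It would be wrong to infer that the TI profiles are distorted in form or that any inference is biased: the SAP makes none.

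**What to change.** - **Derive** hours from injury to each STM dose. Protocol 7.6 has the date and time of site-administered doses recorded in source documents. Take injury time from source or SIFTI-2 records, and flag it where it is approximate.
- **List** the value in Listing 24 beside planned and actual time.
- **Plot** TI Figures 2.2, 2.3 and 2.5 to 2.8 against hours or days since injury, either as the x-axis or as an added axis. For the percent-change figures, the listed hours at entry tell the reader when the denominator was measured.
- **Biomarkers:** do the same for Listing 25 and Figures 4.1 to 4.4 only if SIFTI-2 blood-draw times are available.
- **Tables:** keep planned day. Summaries by visit need a common label, and with three participants the listing supplies the rest.

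The cost is retrieving one time per TI participant and programming one derived variable. Some injury times may be imprecise, but even an approximate time would show whether the three participants entered at similar or very different points after the burn.
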